All subjects in both groups who enroll into this study will undergo an assessment of peripheral endothelial function with reactive hyperemia-peripheral arterial tonometry (RH-PAT) testing using EndoPAT; an assessment of vital signs including heart rate, blood pressure, weight, height and body mass index; laboratory blood work; cardiorespiratory testing using treadmill testing to determine VO₂ max and maximal tolerated heart rate; maximal strength and maximal power

testing on chest press and leg press testing; and ultrasound-based percent body fat and fat distribution testing at baseline, and at 16-weeks follow-up (immediately after completing a 16-week training program using whole body-EMS) (**Figure 1**). Baseline cardiovascular risk factors will be assessed by subject questionnaire and verified by chart review. In addition, subjects will complete an angina/chest pain symptom questionnaire (Rose Questionnaire), quality of life questionnaire (LASA Questionnaire), depression questionnaire (Patient Health Questionnaire-9) and perceived stress questionnaire (Perceived Stress Scale) to assess for psychosocial wellness at each point in the study. Women of childbearing potential will have a urine pregnancy test to rule out pregnancy prior to enrollment. Sensorimotor characteristics such as visual-motor reaction time, Other sensorimotor characteristics (standing balance and posture) will be examined using a force plate and 2D camera with a commercially available app. . . . Standing balance will be assessed by subjects standing on two legs for 30 seconds eyes-open and –closed. . Overhead squatting posture will be examined by analyzing static pictures of performing subjects with ipad-based postural assessment application (Posture Co, Inc, Trinity, FL, USA).

Intervention

Individuals who enroll in this study will be randomized to two groups, in a 1:1 ratio: intervention group and control group. In the intervention group we will apply 16-weeks of conventional whole body-EMS training 1.0 time a week for a maximum of 20 minutes per session, with no intermittent breaks. Individuals will undertake routine exercise maneuvers (including squatting, lunging, forward flexion etc.) under the guidance of certified trainers while simultaneously having percutaneous electrical stimulation applied to their bodies while exercising through the

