and guided by two certified instructor (i.e., two applicants coached by one instructor). Whole body-EMS will be conducted on approximately the same day, once a week (i.e., $1.0 \times \text{week}$) for 20 minutes. The device will apply a bipolar electric current; we will select an impulse frequency of 85 Hz, an impulse width of 350 μs , and will apply an interval approach with 4 seconds of stimulation alternating with 4 seconds of rest. Gentle slight dynamic exercises will be performed during the 4-second stimulation phase. Each session will consist of 10–14 dynamic exercises structured in one to two sets of eight repetitions performed without any additional weights in a standing position. Most exercises will be based on a low amplitude squat exercise ($< 35^\circ$ leg flexion) with full amplitude movements of the arms (such as rowing, lat pulley, or butterfly). The emphasis of the protocol however will not be the effect on muscles induced by voluntary activation but by the application of whole body-EMS with high current intensity during functional movements. During the course of the study, the instructor will progressively increase the volume of stimulation by extending the length of the session from 14 up to 20 minutes after 4 weeks of training. The intensity of the stimulation will be regulated using a rate of perceived exertion (RPE) scale to generate a sufficient, but tolerable, intensity of EMS application to all stimulated areas. For each of the muscle groups stimulated, participants will be encouraged to exercise at a RPE of “6–7 out of 10” (i.e., “hard+ to very hard”) on the Borg CR10 Scale (5). This specification will be achieved in close interaction between the participant and instructor. Based on initial start settings determined after 4, 8, and 12 weeks, the impulse intensity will be increased slightly every 3 minutes to maintain/slightly increase the prescribed RPE during each session (**refer to Supplemental Video**).

Schedule of events

| | Baseline Day 0 | Weeks 1-7 | Week 8 follow-up (+/- 7 days) | Weeks 9-15 | Week 16 follow-up (+/-7 days) |
|---|----------------|-----------|-------------------------------|------------|-------------------------------|
| Informed Consent | X | | | | |
| Brief review of medical history | X | | | | |
| Exercise with EMS device | X | X | X | X | X |
| Blood draw and laboratory testing** | X | | | | X |
| Creatinine Kinase | X | | X | | X |
| Physical Assessment* | X | | | | X |

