Peripheral Endothelial Function: Endothelial function will be measured via the RH-PAT index as previously described (6-9). The studies will be performed in a designated quiet, temperature controlled and uniformly lit room. Individuals in the interventional and control groups will be tested at baseline, and will undergo re-testing after completing 16-weeks of training within their assigned arm (within 2 weeks of completion). Subjects will be fasting for 4 hours before the study and will abstain from coffee or tobacco use on the day of the examination. Subjects taking any vasoactive medications, including calcium channel blockers, nitrates, ACE-inhibitors or beta blockers, will discontinue these for 24 hours prior to testing. The study will be conducted in the sitting position in a comfortable chair with armrests. A fitted blood pressure cuff will be placed on one arm, and the finger cuffs of the Endo-PAT 2000 device (Itamar Medical Inc. Ltd., Caesarea, Israel) will be placed on one finger of each hand (10). Subjects will relax for 10 minutes before initiation of the protocol. Baseline blood pressure and heart rate will be obtained via a digital automated blood pressure cuff (Omrom Healthcare, Inc., Vernon Hills, Illinois). The EndoPAT 2000 will be used specifically in this study because it is a Food and Drug Administration–approved noninvasive device, it allows continuous recording of the signal, and interpretation of the data is operator independent. The use of a control arm will allow the elimination of systemic interference of the test and independence from the participant’s knowledge or conscious control of the signals (10-14). The finger probes consist of inflatable latex air cuffs connected by pneumatic tubes to an inflating device controlled through a computer algorithm. A constant counter pressure

(predetermined by baseline diastolic blood pressure) will be applied through the air cushions. This prevents venous pooling and thereby venoarteriolar reflex vasoconstriction while not occluding arterial blood flow. Pulsatile volume changes of the distal digit induce pressure alterations in the finger cuff, which are sensed by pressure transducers and transmitted to and recorded by the Endo-PAT device. A decrease in the arterial blood volume in the distal fingertip causes a decrease in pulsatile arterial column changes, reflected as a decrease in the measured PAT signal, and vice versa.

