This will be a randomized controlled trial in which there will be an interventional group and a control group into which individuals will be randomly assigned in a 1:1 ratio. We will match individuals, a priori, as best as possible on age (within 5 years) and sex. Baseline, demographic and risk factor distribution will be outlined in Table 1 of our analyses. The following parameters will be measured in all subjects at baseline, and at 16-weeks follow-up (immediately after completing training in either study protocol depending on which group the participant is in): peripheral endothelial function measured with RH-PAT using EndoPAT; body weight and body mass index; waist circumference; blood pressure; total cholesterol, low and high density

lipoprotein cholesterol and triglycerides, fasting blood glucose and HbA1c; high sensitivity-CRP, uric acid, fibrinogen, homocysteine and lipoprotein A; percentage body fat; maximum strength and maximum power in leg press; VO₂ maximum, maximal heart rate, and scores measured on the Rose questionnaire, LASA questionnaire, PHQ-9 questionnaire and Perceived Stress Scale. In addition, serum creatinine kinase will be measured at baseline, 8 weeks and 16 weeks.

We will compare values of each parameter between groups at baseline and after 16-weeks using unmatched analyses (using Student's t-test when comparing the aforementioned measures as continuous variable and using Chi-squared test when characterizing variables in categories of normal vs. abnormal). We will also assess for differences in the value of each parameter within groups between baseline and 16-weeks follow-up using matched analyses (using Student's paired t-test when comparing the aforementioned measures as continuous variable and McNemar's test when characterizing variables in categories of normal vs. abnormal). Lastly, we will compare the differences between baseline and 16-weeks follow-up for each parameter between groups using unmatched analyses (using the student t-test when comparing the aforementioned measures as continuous variable and using Chi-squared test when characterizing variables in categories of normal vs. abnormal).

Clinical Significance

Cardiovascular disease (CVD) is the primary cause for morbidity, mortality, and the associated rising health care costs in the world (21). According to 2012 statistics, poor diet, smoking, and

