| 
Kemmler et al. Evid Based Complement Alternat Med 2016 Effects of Whole-Body Electromyostimulation versus High-Intensity Resistance Exercise on Body Composition and Strength: A Randomized Controlled Trial (3)
 | 
To determine the effectiveness of WB-EMS compared with the gold standard reference HIT, for improving body composition and muscle strength in middle-aged men
 | 
Healthy untrained men, ages 30-50 years N=48
 | 
Randomized controlled trial: healthy untrained men aged 30-50 years were randomly allocated to either HIT (2 sessions/week) or a WB-EMS group (3 sessions/2 weeks) that exercised for 16 weeks HIT was applied as "single-set-to-failure protocol," while WB-EMS was conducted with
 | 
Lean body mass changes of both groups (HIT $1.25 \pm 1.44\%$ versus WB-EMS $0.93 \pm 1.15\%$) were significant ($p = .001$); however, no significant group differences were detected ($p = .395$) Leg-extensor strength also increased in both groups (HIT $12.7 \pm 14.7\%$, $p = .002$, versus WB-EMS $7.3 \pm 10.3\%$, $p =$
 | 
Nil reported
 |

| | | | | | |
|---|--|--|---|---|--|
| | | | intermittent stimulation (6 s WB-EMS, 4 s rest; 85 Hz, 350 ms) over 20 minutes | .012) with no significant ($p = .215$) between-group difference Corresponding changes were also determined for body fat and back-extensor strength | |
| Kemmler, W. et al. Calcified Tissue International 2018 Effects of combined whole body electromyostimulation and protein supplementation on local and overall muscle/fat distribution in older men with sarcopenic obesity: the Franso Study (1) | To determine the combined effect of WB-EMS and protein supplements on local and overall muscle/fat distribution in older man | Community dwelling men ≥ 70 years with sarcopenic obesity N = 67 | Randomized controlled trial: WB-EMS and protein supplementation ($n = 33$) vs. a non-intervention control group ($n = 34$) WB-EMS was conducted 1.5 sessions of 20 | Thigh lean muscle volume increased significantly in the WB-EMS&P ($p < 0.001$) and increased slightly in the CG ($p = 0.435$) Fat volume increased significantly in the CG ($p <$ | 3 participants in each of the WB-EMS&P and control group were lost to follow-up: 1 gave “discomfort during WB-EMS application” as a reason |

| | | | | | |
|--|--------------------------------|--|---|--|---|

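### The week-16 retest is timed from completing training and nothing says whether subjects who stop are retested, so the primary comparison may become completers-only

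*Combined protocol and SAP*

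**What the plan says.** Three places in the combined protocol and SAP tie the follow-up EndoPAT measurement to the end of training.

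- Outcomes and Measurements, Peripheral Endothelial Function: subjects "will undergo re-testing after completing 16-weeks of training within their assigned arm (within 2 weeks of completion".
- Trial Design: assessments are made at baseline and "at 16-weeks follow-up (immediately after completing a 16-week training program using whole body-EMS".
- Statistical Analysis: the 16-week values are taken "immediately after completing training in either study protocol depending on which group the participant is in".

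Laboratory Testing describes the 16-week creatine kinase sample in the same way.

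Other statements point to everyone being measured.

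- The Trial Design sentence begins "All subjects in both groups who enroll into this study will undergo an assessment of peripheral endothelial function".
- The Statistical Analysis sentence reads "The following parameters will be measured in all subjects at baseline, and at 16-weeks follow-up (immediately after completing training in either study protocol".
- Laboratory Testing and Questionnaires refer to all participants at 16 weeks.
- The Schedule of events marks EndoPAT and the other final tests under "Week 16 follow-up (+/-7 days"), with no condition that training was completed.

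The document does not define completion. It gives no rule for subjects who stop after randomisation, no analysis population and no method for missing week-16 values. The only related text is an entry exclusion for people unable to take part or be available for follow-up.

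**The concern.** A subject who stops at, say, week 6 has no completion date, so the retest rule for the primary endpoint gives staff no window in which to test that subject. Staff following it could reasonably skip the visit; staff following the schedule would carry it out. Any value not collected cannot be recovered at analysis.

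Reasons for stopping could differ between the arms. The EMS arm trains under current at a perceived exertion of 6-7 out of 10, while controls receive no or subthreshold current. If subjects who tolerate EMS poorly or respond poorly leave and are not retested, those who remain would look better than the group that was randomised. This would affect the primary endpoint and every secondary endpoint that needs a week-16 value.

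**Working it through.** **Which analyses depend on the retest.** Statistical Analysis plans between-group tests at baseline, between-group tests at 16 weeks, within-group paired tests (paired t, McNemar) and between-group tests of change. All except the baseline comparison need an observed week-16 value. The week-8 creatine kinase sample is not affected.

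**Timing statements side by side.** If training ends at week 16, the schedule's window closes at week 16 + 1 = 17. The endpoint section's window closes at week 16 + 2 = 18. The other two sections say the test follows immediately. Only the schedule's window exists for someone who did not finish.

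**Bias formula.** The plan states no figure to reproduce: the 80 subjects come without a power calculation or a dropout allowance. Let q1 and q0 be the shares stopping without a retest in the EMS and control arms. Let k1 and k0 be the amounts, in SD of change, by which stoppers in each arm do worse than completers. The completers' difference departs from the all-randomised difference by

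bias = q1·k1 − q0·k0.

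It is zero when the shares and the gaps match across arms.

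**Inputs.** From the documents: 80 subjects randomised 1:1, so 40 per arm. Assumed: q1 = 10-20%, k1 = 0.3-0.8 SD, control losses equal in number but uninformative (k0 = 0), and two-sided α = 0.05.

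**Results.** SE = √(2/n) SD with n retained per arm: 0.224 at 40, 0.236 at 36, 0.250 at 32. The upper-tail rate is the probability that a noncentral t with noncentrality bias/SE exceeds the critical value, which is 1.994 on 70 df and 1.999 on 62 df.

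| q1 | k1 (SD) | Bias (SD) | n per arm | Bias/SE | False positive favouring EMS |
|---|---|---|---|---|---|
| none | n/a | 0 | 40 | 0 | 2.5% |
| 10% | 0.3 | 0.03 | 36 | 0.13 | 3.3% |
| 10% | 0.8 | 0.08 | 36 | 0.34 | 5.2% |
| 20% | 0.3 | 0.06 | 32 | 0.24 | 4.2% |
| 20% | 0.8 | 0.16 | 32 | 0.64 | 9.2% |

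If no control is lost (32 against 40), the last row has SE √(1/32 + 1/40) = 0.237, bias/SE 0.67 and a rate of 9.8%. If controls also lose 20% with the same 0.8 SD gap, the bias is 0.20 × 0.8 − 0.20 × 0.8 = 0.

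**Attrition in the documents.** The table of previous studies reports, for a 16-week trial in older men, that "3 participants in each of the WB-EMS&P and control group were lost to follow-up": 3/33 = 9.1% and 3/34 = 8.8%. One participant cited discomfort during stimulation. At 9.1%, with uninformative control losses, the bias would be 0.091 × 0.3 = 0.03 to 0.091 × 0.8 = 0.07 SD.

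**The case against.** The strongest reply is that the plan already covers everyone. Trial Design and Statistical Analysis say all subjects, and the schedule has a calendar visit. On this reading, the references to completing training only describe the expected order of events. A reader might infer from the endpoint section that stoppers are never retested and that the protocol sets a completers-only rule. The documents do not support that: no section withdraws stoppers or excludes them from testing. This part of the reply stands, and the point is therefore conditional.

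The reply does not settle the matter. In both sentences that say all subjects, the 16-week visit is itself explained as following completion, so they do not clearly reach someone who stopped. The most specific rule, the one for the primary endpoint, starts its clock at completion.

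A second reply is that differential stopping is not shown. The cited losses were balanced, even against a non-intervention control. Here the controls wear the same equipment, follow a similar programme and are blinded; intensity is set to be tolerable, and people who cannot take part are excluded at entry. This is fair, and it limits what can be said about size. Equal counts do not exclude bias if the reasons for leaving differ, but the documents give no evidence that they will.

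**Conclusion.** The point holds as a conditional one. The text is inconsistent about the timing of the week-16 tests and silent about subjects who stop, so the primary comparison may become completers-only.

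Under the stated assumptions the bias is 0.03-0.16 SD, against a standard error of 0.22 SD with 40 per arm and 0.24 SD with 36. The false-positive rate favouring EMS is about 3% to 9% instead of 2.5%. The upper end needs both 20% stopping and a 0.8 SD gap, about twice the attrition in the cited trial. With stopping shares and gaps equal across arms there is no bias. The stopping rates and gaps are assumptions, not figures from the protocol. The plan could not check the gap without retesting those who stop. The change is worth making because it is cheap and the missing measurements cannot be obtained later.

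**What to change.** Reconcile Trial Design, Schedule of events, Peripheral Endothelial Function, Laboratory Testing and Statistical Analysis on one rule. RH-PAT and all other week-16 tests are done at week 16, within the schedule's 7 days either side, for every randomised subject whether or not training was completed. Count the weeks from one named origin, either randomisation or the first session. Analyse all subjects by assigned arm, and report the completers' comparison only as a sensitivity analysis, with completion defined in advance. Report by arm how many stopped, how many were not retested and why, and say beforehand how values still missing will be handled.

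The cost is wording changes in several sections and a few extra visits for subjects who are employees at the site. The estimate may be somewhat smaller than among completers. Subjects who decline retesting will still have missing values, so the risk is reduced but not removed.

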- vi) A significant improvement in symptoms of angina as measured by the Rose Questionnaire
- vii) A significant improvement in quality of life as measured by the LASA Questionnaire, symptoms of depression as measured by the PHQ-9 Questionnaire, and symptoms of stress as measured on the Perceived Stress Scale
- viii) No significant difference in blood levels of creatinine kinase across time
- viii) A significant improvement in sensorimotor characteristics (visual-motor reaction time, peak knee muscular force, muscular force steadiness, standing balance, and overhead squatting posture)
- ix)

Methods

Trial Design

This study will consist of a **blinded randomized controlled prospective study design**, and will include 80 healthy individuals who are employees at Mayo Clinic, Rochester MN.

Excluded subjects will consist of:

- Subjects under the age of 18
- Pregnancy/or suspected pregnancy
- Subjects with a history of liver or kidney disease, acute illness, taking medications (such as glucocorticoids)
- Subjects who have conditions (such as chronic inflammatory muscular diseases or Cushing's syndrome) that affect muscle mass

- Individuals with pacemakers and implantable cardiac defibrillators
- Individuals who conduct any other type of resistance training (> 45 minutes/week)
- Individuals who have regular “high” alcohol consumption (> 80g/day on 5 days a week), or are under acute influence of alcohol, drugs narcotics, and/or painkillers
- Subjects unable to consent to or participate in the 16-week EMS intervention or be available for follow up (1).
- Subjects who report recent surgeries
- Cardiac arrhythmias
- Active medical implants
- Epilepsy
- Seizures
- Severe circulatory disorders
- Arterial circulatory disorders
- Strong bleeding tendencies (hemophilia)
- Bleeding
- Abdominal wall hernia
- Inguinal hernia
- Tuberculosis
- Tumor diseases
- Arteriosclerosis in advanced stage
- Severe neurological disorders
- Diabetes mellitus
- Febrile diseases
- Acute bacterial or viral infections
- Liver diseases
- Kidney diseases
- Cardiovascular diseases
- Coronary heart diseases
- Infected or wounded areas of the skin
- Skin cancer
- Rhabdomyolysis

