whole body-EMS machine. Individuals will be trained in a ratio of 2 subjects to 2 machines and one trainer. Subjects in the control group will undergo training with a similar physical exercise program as those in the interventional group undertaking routine exercise maneuvers (including squatting, lunging, forward flexion etc.), and will use the same equipment and will be ‘dressed’ as if they were undergoing whole body-EMS, but will have no/subthreshold electricity signals applied to their body vest. The EMS machine will be switched on and show normal wave patterns suggesting that it is working normally, but study participants will be blinded to whether or not they are receiving percutaneous electrical stimulation while doing the routine exercise maneuvers. This will be applied for a 16-week training program 1.0 time a week for a maximum of 20 minutes per session, with no intermittent breaks. Individuals will be trained in a ratio of 2 subjects to 2 machines and one trainer. Individuals will be randomized to each group, and they and the study investigators will be blinded to the intervention. Otherwise, individuals in both groups will be asked to maintain their normal lifestyles.

In order to generate a safe, individualized, joint-friendly, and time-efficient exercise protocol which will be potentially effective and feasible for a cohort that may have physical limitations, we plan to implement the same previously utilized whole body-EMS training protocol successfully applied in other whole body-EMS trials undertaken in Germany that have focused on body composition and functional parameters (1-4). Briefly, with the whole body-EMS equipment (miha bodytec®, Gersthofen, Germany) we will apply a simultaneous but region specific stimulation of all the main muscle groups with an overall area of up to 2750 cm². We will consistently run an guided whole body-EMS program in groups who will always supervised

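### Arms are matched on age and sex as well as randomised, but both between-arm comparisons ignore the matching, and the plan does not say how matching and randomisation fit together

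*Combined protocol and SAP*

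**What the plan says.** The Trial Design section sets the size: the study "will include 80 healthy individuals who are employees at Mayo Clinic, Rochester MN". The Intervention section states that "Individuals who enroll in this study will be randomized to two groups, in a 1:1 ratio: intervention group and control group", and later that "Individuals will be randomized to each group, and they and the study investigators will be blinded to the intervention". Neither statement mentions pairs, strata or blocks.

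The Statistical Analysis section repeats that there are two groups "into which individuals will be randomly assigned in a 1:1 ratio". Its next sentence reads "We will match individuals, a priori, as best as possible on age (within 5 years) and sex".

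The same section then lists three sets of tests:

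- Between groups, on values: "We will compare values of each parameter between groups at baseline and after 16-weeks using unmatched analyses", by Student's t-test or chi-squared test.
- Within groups: "We will also assess for differences in the value of each parameter within groups between baseline and 16-weeks follow-up using matched analyses", by paired t-test or McNemar's test. The matching here is of a person with himself or herself over time, not of one partner with another.
- Between groups, on change: "Lastly, we will compare the differences between baseline and 16-weeks follow-up for each parameter between groups using unmatched analyses", again by t-test or chi-squared test.

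The documents do not say how matching and randomisation are combined, whether partners are assigned together or in turn, how the sequence is generated or concealed, or what happens to someone without a close match.

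**The concern.** A factor balanced by design should also appear in the analysis. Balancing on age and sex removes part of the chance difference between arms. An unmatched t-test does not know this: its standard error still includes the variation that the design removed. The interval is then wider than it needs to be, and the benefit of matching is not collected. The documents give no power calculation for the 80 subjects, so there is no stated margin against which to set the loss.

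The second issue is how subjects reach their arms. Random assignment does not by itself match anyone, and an age limit of 5 years describes person-to-person matching. Someone therefore has to do something that the plan does not describe, with judgement allowed in how closely it is done. Every between-arm comparison, including the primary one on RH-PAT, rests on that step.

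**Working it through.** There is no figure in the plan to reproduce: alpha, power, effect size and standard deviation are not stated.

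**Inputs from the documents.** 80 subjects at 1:1, so 40 per arm, or 40 pairs if everyone is paired. Both between-arm tests are unmatched.

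**Assumptions.** Two-sided 5% level; within-pair correlation rho of the analysed outcome from 0 to 0.5; for the power figures, a difference of 0.626 SD, which gives about 80% power with 40 per arm.

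**Standard error.** Let each outcome have SD s, with n = 40 pairs randomised within pair.

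- SE used by the unmatched test: s × sqrt(2/n).
- True SE of the difference in means: s × sqrt(2(1 − rho)/n).
- Ratio: 1/sqrt(1 − rho).

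At rho = 0.1 the ratio is 1/sqrt(0.9) = 1.05; at 0.3, 1/sqrt(0.7) = 1.20; at 0.5, 1/sqrt(0.5) = 1.41.

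**Actual error of the nominal 5% test.** Approximately 2 × (1 − Φ(1.96/sqrt(1 − rho))), where Φ is the standard normal distribution function. This gives 0.0388, 0.0191 and 0.0056. A simulation of 100,000 trials per setting, using the t-tests themselves (78 degrees of freedom unmatched, 39 paired), agrees:

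| rho | SE ratio | Type I error, unmatched | Type I error, paired | Power, unmatched | Power, paired |
|---|---|---|---|---|---|
| 0 | 1.00 | 0.050 | 0.049 | 0.79 | 0.78 |
| 0.1 | 1.05 | 0.039 | 0.050 | 0.80 | 0.82 |
| 0.3 | 1.20 | 0.020 | 0.050 | 0.83 | 0.90 |
| 0.5 | 1.41 | 0.006 | 0.050 | 0.87 | 0.97 |

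Unmatched power does not fall as rho rises. What is lost is the gap to the paired column: about 2 points at 0.1, 7 at 0.3 and 10 at 0.5. At rho = 0 nothing is lost.

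The formula is for true pairs. Looser balancing on age and sex would give a smaller version of the same effect.

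**Allocation, as a ceiling only.** Suppose the first of each pair is randomised and the second is placed in the opposite arm. Then 40 of 80 allocations (50%) are determined. Someone who knew the first partner's arm could name (40 × 0.5 + 40 × 1)/80 = 60/80 = 75% of arms correctly, against 40/80 = 50% under simple randomisation. If partners are assigned together, or the first arm stays masked and the sequence is concealed, matching adds no predictability.

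**The case against.** The strongest reply is that matching here may only mean loose balancing of the arms, by stratification or minimisation. No section mentions pairs, and both between-arm tests are deliberately called unmatched, so the authors may not regard participants as paired. That reading is possible. It does not remove the point, because stratification or minimisation on age and sex also calls for those factors in the analysis, and neither method is named.

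The reply is right on size. The correlations are assumed, and nothing in the documents supports a value as high as 0.5. A stable contribution of age and sex to the level of an outcome cancels in a change score, so for the change comparison rho may be near zero and the loss small.

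A reader might infer more: that allocation is predictable and the primary comparison is therefore open to selection bias. The documents do not support this. It would need partners to be assigned in turn, the second one deterministically, and the first partner's arm to be known to someone who influences enrolment. None of these is stated. Trainers are not listed among those blinded, and the instructor sets stimulation intensity together with the participant, so a trainer might well learn the arm; but that is inference, and no section gives trainers a role in enrolment.

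Nor does it follow that a volunteer without a partner within 5 years cannot be randomised, since the matching is only best-effort. It is also not a choice between predictable allocation and wrong standard errors: both, one or neither could apply.

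**Conclusion.** The point holds, in a limited form. The plan matches on age and sex and then ignores both in each between-arm comparison. If the balance is achieved by design, the standard errors are too large by about 5% to 41% over the assumed correlations of 0.1 to 0.5, and the test is conservative, with actual error between about 3.9% and 0.6%. The cost is forgone precision, not extra false positives. It is likely to be small for change scores and larger for week-16 values of any outcome that depends on age or sex.

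The plan also leaves best-effort matching and random assignment unreconciled. That is a gap in the description of allocation. The 40-of-80 figure is the ceiling of one possible procedure and is not evidence that it is used.

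**What to change.** 1. Establish first how subjects are being allocated. The protocol is at Version 6 and does not state enrolment status, so removing the matching sentence without checking could misdescribe what has been done.
2. If pairs are formed and randomised within pair, say so, say how unmatched subjects are handled, and use the pair in the between-arm analysis.
3. If not, replace the matching sentence, for subjects not yet allocated, with wording such as: *Subjects are randomised 1:1 from a concealed, computer-generated list in permuted blocks of varying size, stratified by sex and age band.* Describe separately how subjects already enrolled were allocated.
4. Where pairs are not used, replace the unmatched between-arm t-tests with a linear model (ANCOVA) of the week-16 value on arm, baseline value, age and sex, with RH-PAT as the primary outcome. For normal/abnormal categories, use logistic regression on the same covariates.

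The cost is protocol wording, a stratified list, and regression models in place of simple tests. Age and sex must already be known in order to match on them, so no new data are needed. Age would be balanced by band rather than within 5 years; the age covariate covers most of that difference.
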